The Safety and Efficacy of the Transnasal Humidified Rapid-Insufflation Ventilatory Exchange (THRIVE) for Laser Laryngeal Surgery

Study Protocol

NCT03086265

August 12, 2016

STUDY PROTOCOL: THRIVE AND LASER LARYNGEAL SURGERY

1

STUDY OBJECTIVES

1. DETERMINING THE SAFETY OF THRIVE FOR LASER LARYNGEAL SURGERY. Current practice involves the use of specialized ETTs or jet ventilation catheter (JVC) that are laser resistant, but not laser proof. One of the major concerns with their use is the possibility of airway fire. The “fire triangle” requires the presence of an oxidizer (O_2), the ignition source (laser) and the “fuel” (ETT or JVC). If high oxygen concentration (FiO_2) is administered to the patient, the airway fire may happen, with devastating consequences. Thus, a decrease in oxygen concentration (FiO_2) below 30% constitutes current standard of care when ETT or JVC are used. Such low FiO_2 may not be well tolerated by all the patients.

In contrast, during THRIVE the fuel source (ETT or JVC) is removed, the “fire triangle” is disrupted, and safe administration of a higher FiO_2 is possible. Importantly, a completely “tubeless”, non-instrumented surgical field will be greatly enlarged, providing superior operating conditions and access to all parts of the glottis. This should improve operating conditions, decrease surgical time, and potentially lead to better patient outcomes. The safety of THRIVE for laser laryngeal surgery has not been formally investigated, and will be explored in this study.

2. DETERMINING THE SAFE DURATION OF THRIVE FOR VOCAL CORD LASER SURGERY. With the patient anesthetized, apneic, and adequately oxygenated with THRIVE, the build up of carbon dioxide in patient’s blood ($PaCO_2$) and ensuing acute hypercapnic acidosis will be the main factors limiting the duration of THRIVE administration. At present, the rate of $PaCO_2$ rise with THRIVE is suggested to be between 1.1 – 1.8 mm Hg per minute. By using the serial ABG measurements, we will be able to determine the rate of $PaCO_2$ rise during THRIVE and provide clinical guidance for safe administration of THRIVE in the future. We will allow $PaCO_2$ to rise to 75 mm Hg, which is considered a safe level for moderate hypercapnia in patients without significant comorbidities (see Exclusion Criteria).

3. DETERMINING THE OPTIMAL VENTILATORY STRATEGY FOR MAINTAINING SAFE $PaCO_2$ LEVEL DURING THRIVE ADMINISTRATION

ITRAOPERATIVELY. Once $PaCO_2$ has exceeded 75 mm Hg, we will administer either the low-frequency or high-frequency supraglottic jet ventilation (LFJV, HFJV) through the in situ operating surgical laryngoscope, in order to counteract hypercapnia. The administration of JV modality will be conducted in a randomized fashion, and will continue for at least 10 min, or until $PaCO_2$ has decreased below 65 mm Hg,

STUDY PROTOCOL: THRIVE AND LASER LARYNGEAL SURGERY

2

after which THRIVE will be resumed. The comparative efficacy of these two supraglottic JV modalities in eliminating CO₂ in anesthetized patients is unknown. Determining the optimal mode of JV during THRIVE will allow to establish safe anesthetic protocols for future use. To obtain more robust data, we will cross each patient over to an alternative JV modality, if JV needs to be repeated intraoperatively. For example, if a patient started with supraglottic low-frequency JV, the second JV run will be high-frequency, the third low-frequency again, etc. By having the patient serve as a self-control, we should be able to obtain more robust PaCO₂ data and determine better which frequency works best for counteracting THRIVE-induced deliberate hypercapnia.

4. DETERMINING THE HEMODYNAMIC CHANGES THAT OCCUR DURING THRIVE IN PATIENTS ANESTHETIZED WITH TOTAL INTRAVENOUS ANESTHESIA USING PROPOFOL AND REMIFENTANIL. The administration of THRIVE requires the conduct of total intravenous anesthesia (TIVA), as delivery of anesthetic gases to the patient is not possible. TIVA with propofol and remifentanil is commonly used for VC laser surgery, and will be employed in this study. Acute hypercapnia and hypercapnic acidosis have been shown to produce an increase in cardiac output, cardiac index, a decrease in systemic vascular resistance, without associated tachycardia and myocardial depression with PaCO₂ ≤ 70 mm Hg in patients who do not have significant comorbidities. These hemodynamic responses will be modified by TIVA with propofol and remifentanil, and we will investigate the extent of these changes to determine cardiovascular safety of THRIVE used in conjunction with TIVA. We will be continuously monitoring the heart rate, arterial blood pressure, cardiac output, cardiac index, and systemic vascular resistance during the surgery using Edwards EV1000 Clinical Platform with FloTrack sensor. Determining hemodynamic changes that accompany THRIVE that is conducted under TIVA with propofol and remifentanil will promote safe use of this technique in clinical anesthesia practice. Using Edwards EV1000 Clinical Platform we also will assess acute hemodynamic changes that may be associated with supraglottic LFJV and HFJV under the conditions of deliberate moderate hypercapnia. Demonstrating the safety and efficacy of THRIVE may make this technique a simple, safe and effective alternative to conventional use of ETT or JV during laser laryngeal surgery in selected patients.

EXCLUSION CRITERIA

1. Patients with significantly decreased myocardial function (ejection fraction < 50%)
2. Patients with abnormal cardiac rhythm and conduction abnormalities, except for patients with isolated, asymptomatic premature atrial and ventricular contractions.
3. Patients with significant peripheral vascular disease, such as those with the symptoms of intermittent claudication.
4. Patients with known significant cerebrovascular disease, such as history of cerebrovascular accidents (CVAs) and transient ischemic attacks (TIAs).
5. Patients with significant renal insufficiency, as manifested by estimated glomerular filtration rate (eGFR) < 60 ml/min/1.73 m².
6. Patients with electrolyte (K+, Ca++) abnormalities, as determined by the lab values outside of a normal range.
7. Patients with the history or symptoms of increased intracranial pressure or reduced intracranial compliance (e.g. headaches, nausea and vomiting, visual changes, mental changes).
8. Patients with skull base defects.
9. Patients with pulmonary hypertension who have pulmonary artery pressures above the normal range.
10. Patients with significant chronic obstructive or restrictive lung diseases, as manifested by known history of baseline chronic hypoxia and/or hypercapnia, and/or baseline room air SpO₂ < 95%.
11. Obese patients with BMI > 35 kg/m².
12. Patients with severe and poorly controlled gastroesophageal reflux disease despite medical treatment.
13. Patients with hiatal hernia and full stomach patients.
14. Patients on immunosuppressive medications.
15. Patient's refusal to participate in the study.
16. Patients who do not understand English or mentally handicapped.
17. Pregnant or breastfeeding patients.

STUDY PROTOCOL: THRIVE AND LASER LARYNGEAL SURGERY

PROTOCOL AT A GLANCE AND STUDY END-POINTS

18. Patients will be randomly assigned to either THRIVE or Control group (conventional management with laser ETT or jet ventilation catheter – infraglottic jet ventilation – if required). Patients within THRIVE group will be further randomly assigned to either low- or high-frequency supraglottic JV for intraoperative $\text{PaCO}_2 > 75 \text{ mmHg}$.
19. Patients in both groups will have peripheral A-line started prior to induction. Central hemodynamic parameters will be monitored using Edwards system.
20. Patients in THRIVE group will be monitored with serial ABGs, to determine changes in PaO_2 , PaCO_2 , and electrolytes.
21. Anesthetic management is standardized for both groups.
- 22. For both groups, and particularly for THRIVE, assure fully moistened pledgets, and no cotton material/other fuel left in airway before firing the laser.**
23. Study end-points:
 - a. THRIVE GROUP
 - i. Changes in PaO_2 , PaCO_2 , pH, electrolytes, and FiO_2 (tracheal)
 - ii. Hemodynamic changes during permissive hypercapnia
 - iii. Comparative effectiveness of JV modalities on CO_2 elimination
 - iv. Comparative effect of JV modalities on hemodynamics during permissive hypercapnia
 - b. BOTH GROUPS
 - i. Total apnea time
 - ii. Anesthesia time: from induction to awake (opening eyes to command)
 - iii. Surgical time: from picking up suspension laryngoscope to laryngoscope withdrawal
 - iv. Time to suspension: from picking up suspension laryngoscope to full suspension
 - v. Number of required repositions for suspension laryngoscope
 - vi. Lowest SpO_2
 - vii. Total doses of anesthetic drugs used, including vasopressors, etc.
 - viii. PACU recovery profile
 - ix. Functional recovery profile after surgery

STUDY PROTOCOL: THRIVE AND LASER LARYNGEAL SURGERY

OPERATING ROOM PREPARATION

1. All drugs, airway supplies, suction, eye tape, etc. per routine.
2. 5.0 laser ETT with two pre-filled 10 ml NS syringes: use a methylene blue tinged syringe for a proximal cuff.
3. A long pediatric ETT stylet and a pediatric gum-elastic bougie.
4. 5.0 MLT tube for apneic intermittent ventilation (AIV), if required (see protocol, below).
5. Precut large Tegaderm strips for securing ETT to the chin in left corner of patient's mouth.
6. Video laryngoscopy system: either a Glidescope or a Storz CMAC system.
7. Monsoon JV with connection tubing for suspension laryngoscope, and full humidification set up.
8. Sterile tracheal suction catheter assembly for tracheal FiO_2 sampling.
9. Four channel Alaris pump with:
 - a. NS carrier at 50 ml/hr
 - b. Propofol drip
 - c. Remifentanil drip
 - d. Check to assure tight connections throughout
10. IV LR/NS loading 5 ml/kg prior to induction, and 5 ml/kg x 1 as required intraop.
11. 20 ml NS syringe in line for chasing the induction and IVP drugs intraop. **Please minimize total IVF due to high incidence of urinary retention in male patients.**
12. Edwards system.
13. I-STAT with sufficient number of cartridges.
14. Working PNS with pads (make sure the battery is fresh).
15. BIS/Sedline monitor.

STUDY PROTOCOL: THRIVE AND LASER LARYNGEAL SURGERY

	THRIVE GROUP	CONTROL GROUP
PREOP and PREMEDICATION	
 • Obtain patient's consent. Make 2 copies: one for the chart, and another for the patient. • Place a copy of consent into patient's folder, together with postop diary. Place patient's sticker on folder. • Give a surgeon a folder with postop QoR15. Place patient's sticker on folder. • Your study folder should contain consent, preop QoR15, intraop and PACU data collection sheets. Place patient's sticker on folder. • Randomize the patient to either THRIVE or CONTROL group. • Obtain preop QoR15 and VAS pain score. • Peripheral IV, 20 g R upper extremity (preferred), tape securely straight out. • Midazolam 0.007 mg/kg incremental doses to achieve sufficient anxiolysis, not to exceed 0.025 mg/kg total dose, unless severe anxiety. For elderly patients (70-80 y.o), limit total dose of Midazolam to 0.5 mg. • Start an awake A-line for both groups in OR, and draw baseline ABG and i-STAT Troponin I level #1 for THRIVE group only. 	
PRE-INDUCTION: CONSECUTIVE STEPS	
Start with OR table 180°.
 
Place standard ASA monitors, BIS/Sedline, and peripheral nerve stimulator (TOF ulnar nerve).
 
Connect A-line to Edwards EV1000 Clinical Platform for automated monitoring of ABP, HR, CO/CI, SVR.
 
 • Pre-O₂ with THRIVE (FiO₂ 1.0) at 40 l/min for 5 min. • Maintain patient's head is elevated 30-40° (table in BACK UP position, not reverse Trendelenburg). • Obtain ABG after 5 min of THRIVE, per THRIVE protocol. 	
OR table in standard position.
 
Preoxygenate for 5 min or until FeO₂ > 0.9.

	
 • Pre-induction: 
 ○ IV fluid loading completed: 5 ml/kg. ○ IV Glycopyrrolate 0.2 mg if HR ≤ 50 bpm for elderly patients (70-80 y.o.). ○ Assure all surgical supplies are ready for immediate use in THRIVE group. ○ Both anesthesia and surgical time-outs completed. 	

STUDY PROTOCOL: THRIVE AND LASER LARYNGEAL SURGERY

7

INDUCTION	
 IV Remifentanil 1 mcg/kg, Propofol 2mg/kg IV, Rocuronium 1.2 mg/kg IV, no IV lidocaine. Additional Remifentanil 0.5 mcg/kg and/or Propofol 0.5 mg/kg IV boluses, as required during video or suspension laryngoscopy, per hemodynamic responses and BIS/Sedline readings. Obtain tracheal FiO₂ once patient is suspended, before the start of surgery, per THRIVE protocol. 	
	
 Turn THRIVE to 70 l/min. Maintain jaw thrust, with oral airway as necessary, before surgeon starts suspension laryngoscopy. Continue, as necessary until patient is in full suspension. Suspension laryngoscopy by surgeon in 1 min. 	
 Mask ventilation, if required. Intubate in 1 min with laser 5.0 ETT, using acute angle video laryngoscopy system (Glidescope or Storz D-blade), secure ETT to chin in left corner of the mouth.
MAINTENANCE	
 TIVA + THRIVE (FiO₂ 1.0) at 70 l/min. If SpO₂ < 90%, or ventricular arrhythmias, discuss with surgeon converting to the following options: 
 Supraglottic or Infraglottic JV 5.0 laser ETT 5.0 MLT tube with apneic intermittent ventilation Obtain ABGs per THRIVE protocol. If PaCO₂ > 75 mmHg, randomize patients to JV protocol, and institute JV accordingly. Crossover each patient to an alternative JV frequency for repeated JV rounds. 	
 TIVA + O₂:Air; FiO₂ < 0.3 Mechanical ventilation to normocapnia: EtCO₂ 35-40 mmHg. Vt 8 ml/kg of predicted body weight (PBW), PEEP 5 cmH₂O. PBW Males = 50 + 2.3 (Height" - 60) PBW Females = 45.5 + 2.3 (Height" - 60) FiO₂ < 0.3 unless SpO₂ < 90% (increase FiO₂ to 0.4, and coordinate subsequent FiO₂ decrease with surgeon during laser timeout).
	
 A-line and Edwards monitoring. No NBP monitoring, unless A-line malfunction. BIS-guided TIVA with Propofol/Remifentanil to maintain BIS 40-60. Maintain main IV at TKO. All IV bolus drugs are chased by 15 ml of NS using in-line 20 ml syringe. 	

MAINTENANCE
(cont.)

- **TIVA dosing:**
 - TIVA is carried in by Alaris NS carrier at 50 ml/hr.
 - For normal weight patients, dose Prop/Remi infusions per total body weight.
 - For obese patients (BMI \geq 30), dose Prop/Remi infusions per lean body weight (LBW). **Simplified LBW formula: LBW = IBW x 1.2; IBW = 22 x Ht(m)².**
 - **Starting dose:** Propofol 120 mcg/kg/min, Remifentanil 0.1 mcg/kg/min.
 - **Titratable range:** Propofol 80-150 mcg/kg/min, Remifentanil 0.05-0.3 mcg/kg/min. **Optimize Remifentanil dose first.**
 - Rocuronium boluses 0.15 mg/kg, to maintain 0-1/4 TOF at ulnar nerve.
- **Treating hypertensive responses (MAP $>$ 20 mmHg from preoperative baseline):**
 - Remifentanil 0.5 mcg/kg and Propofol 0.5 mg/kg boluses q 2 min, as required per hemodynamic responses and BIS/Sedline readings
 - Labetalol 0.07 mg/kg boluses q 10 min up to a total dose of 1 mg/kg, as required per hemodynamic responses and BIS/Sedline readings
 - Fentanyl 0.5 mcg/kg IV bolus, total dose limit 1 mcg/kg, **only** if perceived need for additional analgesia after Remifentanil infusion had been maxed out at 0.3 mcg/kg/min
- **Treating hypotensive responses (MAP $<$ 20 mmHg from preoperative baseline):**
 - Crystalloid loading 5 ml/kg x 1
 - Ephedrine 5 mg IV if HR $<$ 60 bpm, or Phenylephrine 100 mcg IV if HR $>$ 60 bpm. Repeat x 2 in escalating doses if no response: Ephedrine (10 mg, 20 mg q 1 min), or Phenylephrine (200 mcg, 400 mcg q 1 min).
 - Vasopressin 1 unit IVP if no response to Ephedrine/ Phenylephrine, repeat x 2 prn.
 - Phenylephrine drip, start at 0.3 mcg/kg/min, increase in 50% increments
- **Obtain tracheal FiO₂ before withdrawal of suspension laryngoscope, per THRIVE protocol.**

STUDY PROTOCOL: THRIVE AND LASER LARYNGEAL SURGERY

9

EMERGENCE	
• Zofran 4 mg IV.• Reverse NMB with Sugammadex, as following: 2 mg/kg for TOF 1-2/4; 4 mg/kg for TOF 0/4, with postetanic count of 1-2. Administer additional Sugammadex 2 mg/kg, if 4 mg/kg not fully effective.• Discontinue TIVA upon completion of surgery.• Transport to PACU: FMO₂ at 6 l/min.
	
• Maintain THRIVE at 70 l/min with jaw thrust ± oral airway as required, until return of spontaneous ventilation and consciousness. Mask ventilation, if required.• Obtain ABG and Troponin I level #2, once patient resumes spontaneous ventilation, per THRIVE protocol.
STANDARDIZE POSTOP ORDERS	
• IV Fentanyl 25 mcg boluses q 5 min prn VAS ≥ 4, total dose 250 mcg.• PO Hydrocodone-acetaminophen (NORCO) 5-325 mg, 1 tab prn VAS ≥ 4, may repeat x 1.• If allergic to NORCO, Oxycodone-acetaminophen (PERCOCET) 5-325 mg, 1 tab prn VAS ≥ 4, may repeat x 1.• IV Demerol 12.5 mg for shivering only, may repeat x 1.• Treatment of PONV:
◦ Zofran 8 mg IV x 1◦ If no effect, and no contraindications, add IV Promethazine 12.5 mg x 1
PACU DATA COLLECTION	
• Obtain PACU data collection sheet.• Discontinue A-line once the last ABG and Troponin I are drawn 1 hr after resumption of spontaneous ventilation, per THRIVE protocol.
EDWARDS DATA COLLECTION	
• Download Edwards data to flash drive, selecting 20 sec download interval, before starting next case.

STUDY PROTOCOL: THRIVE AND LASER LARYNGEAL SURGERY

10

THRIVE PROTOCOL	
PREOP	
• Obtain baseline ABG and i-STAT Troponin I #1.
PREINDUCTION	
• Pre-O₂ with THRIVE (FiO₂ 1.0) at 40 l/min for 5 min.• Maintain patient's head is elevated 30-40° (table in BACK UP position, not reverse Trendelenburg).• Connect OR monitors and Edwards system.• Obtain ABG after 5 min of THRIVE @ 40 l/min.
INDUCTION	
• THRIVE @ 70 l/min.• Maintain jaw thrust, with oral airway as necessary, for 1 min before surgeon starts suspension laryngoscopy.
MAINTENANCE	
• Maintain THRIVE @ 70 l/min.• Obtain tracheal FiO₂ once patient is suspended, before the start of surgery.• Assure fully moistened pledges, and no cotton material/other fuel left in airway before firing the laser.• ABG q 10 min post-induction, until patient resumes spontaneous ventilation.• Once PaCO₂ > 75 mmHg, randomize patients to low-frequency (20 cpm) or high-frequency (150 cpm) supraglottic jet ventilation
○ Settings for either JV modality:
▪ DP (driving pressure, psi) = total body weight x 0.4 (do not exceed 45 psi)▪ FiO₂ 1.0, Inspiratory time 40%, Humidity level: maximum (8)○ Continue JV, checking ABG q 10 min, until PaCO₂ reaches ≤ 65 mmHg, at which point resume THRIVE○ Repeat JV per above, as necessary for PaCO₂ > 75 mmHg. Crossover each patient to an alternative JV frequency for repeated JV rounds.• Obtain tracheal FiO₂ once surgery completed, before withdrawal of suspension laryngoscope.
EMERGENCE	
• Maintain THRIVE at 70 l/min with jaw thrust ± oral airway as required, until return of spontaneous ventilation and consciousness. Mask ventilation, as necessary.• Obtain ABG and i-STAT Troponin I #2 once patient resumes spontaneous ventilation.
PACU	
• Obtain ABG and i-STAT Troponin I #3 one hr after resumption of spontaneous ventilation. Remove A-line.

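### The protocol calls 75 mm Hg the safe PaCO2 limit, but its 10-minute sampling rule detects crossings on average in the low 80s, and possibly as high as 86–93

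*Protocol*

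**What the plan says.** Study Objectives, item 2, says PaCO2 will be allowed "to rise to 75 mm Hg, which is considered a safe level for moderate hypercapnia in patients without significant comorbidities". The same item gives the rate of rise on THRIVE, which "is suggested to be between 1.1 – 1.8 mm Hg per minute", and promises to "provide clinical guidance for safe administration of THRIVE in the future".

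The operating rule is in item 3: once PaCO2 "has exceeded 75 mm Hg, we will administer either the low-frequency or high-frequency supraglottic jet ventilation". The end-points list (item 18) and the Maintenance rows of the two procedure tables give the same trigger, above 75. The Maintenance row of the THRIVE Protocol table sets the sampling: "ABG q 10 min post-induction, until patient resumes spontaneous ventilation". THRIVE resumes after jet ventilation once PaCO2 is 65 or lower.

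The other conversion rule in the THRIVE arm does not depend on CO2: "If SpO₂ < 90%, or ventricular arrhythmias, discuss with surgeon converting to the following options". An end-tidal CO2 target appears only in the control column.

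On tolerance, item 4 cites haemodynamic responses "without associated tachycardia and myocardial depression with PaCO₂ ≤ 70 mm Hg in patients who do not have significant comorbidities". End-point 23.a.i covers changes in PaCO2 and other blood-gas values. It names neither the highest PaCO2 nor the time above 75.

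**The concern.** The objective presents 75 as the level PaCO2 may reach. In the procedures it is a level that must already have been passed, and been seen on an intermittent sample, before anyone acts. Between samples PaCO2 keeps rising and the protocol specifies nothing to detect it. The exposure the rules produce is therefore higher than the one the safety statement describes, and further still above the 70 mm Hg to which the cited tolerance extends.

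Two things are at stake. Patients in longer cases are exposed to more hypercapnia than the protocol says. And objective 2 is meant to yield guidance on safe use, which would be wrong if it quoted 75 as the exposure tested. The triggering gas does record the overshoot, so the data are not lost, but the outcome that would display it is not named.

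**Working it through.** The plan gives no expected PaCO2 at detection, so there is no figure of its own to reproduce.

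**Inputs from the protocol.** Threshold 75 mm Hg; rate r = 1.1–1.8 mm Hg/min (midpoint 1.45); sampling interval 10 min; restart level 65; cited tolerance up to 70.

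**Assumptions.** Linear rise, with the crossing of 75 equally likely at any point in the 10 minutes.

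**At detection**

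| Quantity | Formula | r = 1.1 | r = 1.45 | r = 1.8 |
|---|---|---|---|---|
| Rise between gases | 10r | 11 | 14.5 | 18 |
| Mean PaCO2 at detection | 75 + 5r | 80.5 | 82.25 | 84.0 |
| Upper bound | 75 + 10r | 86 | 89.5 | 93 |
| Share detected above 80 | 1 − 5/(10r) | 54.5% | 65.5% | 72.2% |
| Mean minutes above 70 before detection | 5/r + 5 | 9.5 | 8.4 | 7.8 |
| Maximum minutes above 70 | 5/r + 10 | 14.5 | 13.4 | 12.8 |

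Mean time above 75 before detection is 5 min at any rate. Each minute spent waiting for the gas result and setting up the jet adds a further 1.1–1.8 mm Hg, which is not counted here. After a jet round, THRIVE restarted at exactly 65 reads 65 + 10r = 76–83 at the next gas.

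**Does the even-crossing assumption drive the result?** Gases fall at fixed times (10, 20, 30… min), so the starting PaCO2 matters, and the documents do not give it. I simulated the fixed schedule with the rate uniform on 1.1–1.8 and assumed starting values:

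| Assumed start (mm Hg) | Mean at detection |
|---|---|
| 35 | 82.6 |
| 40 | 83.3 |
| 45 | 81.4 |
| 50 | 81.5 |

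With starts spread evenly over 35–45, the mean is 82.7 (5th–95th percentile about 75.7–90.3) and 66% are detected above 80. About 13% of these patients are detected by the 20-minute gas, at a mean of 77, so the low 80s describes longer cases.

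**Closer sampling.** A reading of 57 or less cannot exceed 75 within 10 min at 1.8 mm Hg/min or slower (57 + 18 = 75). With 5-minute gases once a reading exceeds 57, the mean at detection is 75 + 2.5r = 77.75–79.5 and the bound is 75 + 5r = 80.5–84.0. The fixed-schedule simulation gives means of 78.4–78.8 and a maximum below 84. Gases needed to detect the first crossing, current rule against 5-minute rule, are 3.33 against 4.11 (start 35), 3.02 against 3.60 (40), 2.57 against 3.57 (45) and 2.21 against 3.02 (50): 0.6–1.0 extra.

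**The case against.** The strongest reply is that the procedures are consistent and open: every operating rule says above 75, and the 10-minute interval is printed. On that reading the sentence in objective 2 is shorthand for the intervention threshold; it never calls 75 a ceiling. Nothing in the documents shows that a few minutes in the low 80s is harmful in patients selected by these exclusions. Heart rate, arterial pressure and cardiac output are monitored continuously, troponin is measured serially, and arrhythmia or desaturation prompts conversion. The gap between 70 and 75 would remain even with continuous CO2 monitoring. The rate is only suggested, and measuring it is part of objective 2. Individual values vary widely: a start of 40 is detected at 84.0 at 1.1 mm Hg/min but at 76.0 at 1.8. The number crossing could be very small.

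Much of this stands. No harm is shown, individual values run from just above 75 to the low 90s, and the number affected is unknown. The monitoring would reveal consequences of hypercapnia, but it does not limit PaCO2. Reading 75 as a trigger is correct for the procedures, and that is why the objective should say so. The design also plans for these patients, since the jet-ventilation randomisation and crossover exist only for those who pass 75. The gap from 70 to 75 is a weakness in the safety rationale separate from sampling, and the overshoot widens it.

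**Conclusion.** The concern holds. As written, the rules do not keep PaCO2 at the level the protocol calls safe. Among patients who cross 75, mean PaCO2 at detection is about 82 mm Hg (80.5–84.0 by rate), with an upper bound of 86–93. This rests on a linear rise at the protocol's suggested rate, no unscheduled gases, and crossings spread evenly over the interval; the fixed-schedule means of 81.4–83.3 show that the last condition is not critical. The bound would be higher if the true rate exceeded 1.8.

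The conclusion covers only cases long enough to cross. From assumed starts of 35–45 that takes about 17 min (30/1.8) to 36 min (40/1.1) of apnoea. The THRIVE arm is about 10 patients (20 randomised 1:1) and no surgical duration is given, so the count cannot be estimated. The randomised comparisons are not affected. The point deserves correction because it concerns a stated safety level and the remedy is cheap.

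**What to change.** 1. In objective 2, replace the sentence allowing a rise to 75 with wording such as: *PaCO2 above 75 mm Hg on a 10-minute gas is the action level for jet ventilation; at a rise of 1.1–1.8 mm Hg/min, PaCO2 at detection is expected in the low 80s, with an upper bound of 86–93 mm Hg.* Extend the safety rationale to that range.

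2. Add to list 23.a the highest measured PaCO2 per patient, described as a lower bound on the true peak. Minutes above 75 during THRIVE apnoea is a useful but optional companion: interpolate linearly between gases, then extend at the last slope from the triggering gas to the recorded start of jet ventilation. Do not interpolate across the jet start. With an assumed 3-minute delay and a fall to 65 after 10 min of jet ventilation, a straight line counts 4.6–6.2 min above 75 after the trigger, against 7.7–8.9 min.

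3. Recommended: during THRIVE apnoea, draw gases every 5 minutes once a reading exceeds 57, and change the figures in step 1 to a mean of 77.8–79.5 and a bound of 84. A restart at exactly 65 is not helped, because it still reads 76–83 at 10 minutes, but it stays within that bound.

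**Cost.** Steps 1 and 2 need a wording amendment, two derived outcomes and a jet-start time (the data sheets may already record it), with no extra blood. Step 3 adds about 0.6–1.0 gas per first crossing from the existing arterial line. The stated safety figure becomes less favourable. The SAP is written in the past tense; if enrolment has ended, step 3 no longer applies, but the report should still call 75 an action level and give the highest measured PaCO2.

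### The preop QoR-15 is collected but enters no analysis the SAP states, and nothing requires that self-reported baseline to be taken before allocation is disclosed

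*Protocol*

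**What the plan says.** The Preop and Premedication row of the protocol table contains, in adjacent bullets, "Randomize the patient to either THRIVE or CONTROL group" and then "Obtain preop QoR15 and VAS pain score". The same row provides for the postoperative measurement ("Give a surgeon a folder with postop QoR15") and mentions a folder with the consent copy "together with postop diary". It also lists "intraop and PACU data collection sheets" among the study papers.

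That row is not described as a sequence. Only the row after it carries such a label: "PRE-INDUCTION: CONSECUTIVE STEPS". No section says when the patient, or the person collecting the form, learns the allocation, and no blinding is described.

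The end-point list for both groups includes "Functional recovery profile after surgery" (item 23.b.ix) without naming an instrument, time point or metric. The PACU row says "Obtain PACU data collection sheet", but the sheet is not reproduced.

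The SAP has a single analysis sentence. It covers anesthesia, surgical and recovery outcomes with descriptive summaries, a 2-sided t-test and a Fisher exact test. It names no score and no covariate. The sample size was planned as 40 and cut to 20, allocated 1:1.

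**The concern.** There are two linked issues.

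First, a baseline of the same instrument is collected and then plays no part in the stated analysis. In a trial of 20, precision is scarce, and adjusting the postoperative score for its own baseline is the usual inexpensive way to recover some. Because both scores exist and the SAP does not choose between them, the t-test could also be run on change scores, whose performance here ranges from much worse to much better than that of postoperative scores.

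Second, QoR-15 and VAS pain are self-reported. If a patient already knows the arm when completing the baseline, the answer may shift. A change score or a baseline-adjusted analysis would then carry that shift into the treatment comparison. Taking the baseline first costs nothing and removes the question. Surgical time, apnea time and lowest SpO2 are not affected by either issue.

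**Working it through.** **Inputs from the documents.** N = 20, 1:1, so 10 per arm; 2-sided t-test (SAP). Preoperative and postoperative QoR-15 both collected (Protocol, Preop and Premedication). The SAP gives no alpha, power, effect size or SD behind 40 or 20, so there is no stated figure to reproduce.

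**Assumptions.** 2-sided alpha 0.05; normal scores with equal SD before and after surgery, set to 1; pre-post correlation r, not in the documents, taken from 0 to 0.7; a difference of 1 SD for illustration.

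**Precision.** Variance of the arm difference relative to the postoperative t-test:
- change score: 2(1 − r)
- ANCOVA: (1 − r²)(1 + 1/(N − 4)) = (1 − r²) × 17/16

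Break-even for ANCOVA in variance: (1 − r²) × 17/16 = 1, so r² = 1/17 and r = 0.243.

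**Power for 1 SD.** Postoperative t-test: noncentrality √(10/2) = 2.236 on 18 df, giving 56.2%. ANCOVA at r = 0.5: ratio 0.75 × 1.0625 = 0.797, noncentrality 2.236/√0.797 = 2.505 on 17 df, giving 65.6%. The table shows values from 200,000 simulated trials per setting; the formulas agree to within half a percentage point.

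| r | ANCOVA/t-test variance | ANCOVA power | Change-score power | Postop t-test power | ANCOVA mean 95% half-width (t-test 0.93 SD) |
|---|---|---|---|---|---|
| 0 | 1.06 | 54% | 32% | 56% | 0.96 SD |
| 0.3 | 0.97 | 58% | 43% | 56% | 0.91 SD |
| 0.5 | 0.80 | 66% | 56% | 56% | 0.83 SD |
| 0.7 | 0.54 | 82% | 78% | 56% | 0.68 SD |

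Against the t-test, ANCOVA therefore loses about 3 points at r = 0 (56.2 to 53.6), gains about 1 point at r = 0.3 and gains about 25 points at r = 0.7 (56.2 to 81.7). For a 0.5-SD difference the t-test has 18.5% power and ANCOVA has 18, 19, 22 and 30%.

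**If the baseline were taken after disclosure (illustration only).** Let knowledge of the arm shift one arm's baseline by d SD, with a fraction k of that shift persisting after surgery, and no true effect. The mean errors are k·d (postoperative only), (k − 1)·d (change) and (k − r)·d (ANCOVA). No method is free of error for every k. With d = 0.5 and r = 0.5, false-positive rates (postoperative / change / ANCOVA) are:
- k = 0: 5 / 19 / 9%
- k = 0.5: 8 / 8 / 5%
- k = 1: 19 / 5 / 9%

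Over r = 0.3 to 0.7 and k = 0, 0.5 and 1, the worst cases are 19 / 28 / 17% at d = 0.5 and 8 / 11 / 8% at d = 0.25. Neither d nor k is in the documents, so these rates show the direction and ordering of the problem. They do not measure it in this trial.

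**The case against.** The case against has real force on several points.

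- The SAP never mentions QoR-15. Its wording on recovery outcomes could equally cover recovery times, diary items or event counts. That stands: the link from QoR-15 to the functional recovery end-point is inferred. What the documents do establish is that the score is collected twice and no analysis uses the baseline.
- A reader might infer from the bullet order that the baseline was taken after the patient knew the arm. The documents do not support that. Randomizing a patient is not the same as telling the patient, the list mixes folder preparation with patient steps, and only the following row is marked as consecutive. What remains is a missing safeguard, with no evidence of a biased baseline.
- A reader might also infer that the planned t-test is wrong, or that ANCOVA is always better. Neither follows. An unadjusted comparison of postoperative scores in a randomized trial is valid, and at 10 per arm ANCOVA costs power when r is near zero.
- Where precedence cannot be shown, one can argue for the postoperative t-test as the main result, since it carries no error if a persistent shift is counted as part of the effect of assignment. Yet on the d = 0.5 grid ANCOVA has the lowest worst case (17%, against 19% and 28%). The choice depends on what is being estimated, and the documents do not settle it.
- The SAP is dated February 2020 and written in the past tense, so little may still be changeable. That limits the checklist edit but not the reporting.

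**Conclusion.** The concern holds in a limited form. The collected preoperative QoR-15 enters no stated analysis, and no rule places it before disclosure of allocation. At 10 per arm, adjusting for it would change power for a 1-SD difference by between about −3 and +25 points as r runs from 0 to 0.7, with break-even near 0.24. The size rests on an assumed r, equal SDs and normal scores. The false-positive rates rest additionally on assumed d and k and are illustrative. No recovery score is named primary, and whether a postoperative VAS exists as an outcome cannot be judged, because the PACU sheet is not shown. This is worth considering as an inexpensive improvement and a point to report; confidence is medium.

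**What to change.** 1. For any patient still to be enrolled, move "Obtain preop QoR15 and VAS pain score" ahead of "Randomize the patient to either THRIVE or CONTROL group", or require it to be completed before allocation is disclosed to the patient or the person collecting the form. If enrolment is over, this step is moot.
2. Add to the SAP: postoperative QoR-15, at a named time point, will be compared by ANCOVA with arm and preoperative QoR-15, reporting the adjusted mean difference and 95% CI beside the unadjusted postoperative t-test. Label the ANCOVA post hoc if the data have been seen.
3. Report when the baseline was taken relative to disclosure. If precedence cannot be shown, give both the unadjusted postoperative and the ANCOVA results with that caveat, do not rely on change scores alone, and do not present either result as settled. Note too that, with no blinding described, the postoperative self-report may also reflect knowledge of the arm.

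The cost is a few sentences and no new data. ANCOVA uses one degree of freedom and adds about 6% to the variance if r = 0.
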